Official Title: Bovine Carotid Artery Biologic Graft and Expanded Polytetrafluoroethylene for Permanent Hemodialysis Access

NCT03300024

Document Date: 10/15/2015

JHM IRB - eForm A – Protocol

A Prospective Randomized Study of Bovine Carotid Artery Biologic Graft and Expanded Polytetrafluoroethylene for Permanent Hemodialysis Access

Protocol Version: Version 1 (IRB00069002)

Protocol Date: 10/15/2015

Type of Study: Investigator initiated study. The principal investigator will have sole responsibility for monitoring and oversight of problem/events for this research.

Institution: Johns Hopkins Medical Institutions, Baltimore, MD, USA

1. Abstract

Arteriovenous grafts (AVG) remain reliable substitutes for permanent hemodialysis access in scenarios that preclude the placement of arteriovenous fistulae. There is scarcity of evidence to support the current preference of synthetic conduits over biologic grafts in clinical practice. Advances in the design of AVG's warrant contemporary comparisons between synthetic and biologic AVG options. This is especially important as biologic conduits may confer an advantage by virtue of their inherent similarity to the native human vasculature. We propose a randomized study to compare bovine carotid artery (BCA) biologic grafts and expanded polytetrafluoroethylene grafts (ePTFE) for permanent hemodialysis access.

2. Objectives

The overall goal of this project is to compare the one and two year patency, complication and intervention rates between BCA and standard ePTFE.

Specific Aim 1: To compare functional primary patency between BCA and ePTFE

Hypothesis 1A: Patients receiving BCA grafts will have a higher primary patency rate at 1 and 2 years follow up than those who receive ePTFE grafts.

Specific Aim 2: To compare functional primary assisted patency between BCA and ePTFE

Hypothesis 2A: Patients receiving BCA grafts will have a higher functional primary assisted patency rate at 1 and 2 years follow up than those who receive ePTFE grafts.

Specific Aim 3: To compare functional secondary patency between BCA and ePTFE

Hypothesis 3A: Patients receiving BCA grafts will have a higher functional secondary patency rate at 1 and 2 years follow up than those who receive ePTFE grafts.

Specific Aim 4: To compare complication (pseudoaneurysms, infection and steal syndromes) rates between BCA and ePTFE

Hypothesis 4A: Patients receiving BCA grafts will have lower complication rates at 1 and 2 years follow up than those who receive ePTFE grafts.

Specific Aim 5: To compare re-intervention rates between BCA and ePTFE

Hypothesis 5A: Patients receiving BCA grafts will have a lower re-intervention rate at 1 and 2 years follow up than those who receive ePTFE grafts.

Primary outcomes: Primary, primary assisted and secondary patency rates at 1 and 2 years.

Secondary outcomes: Complication (pseudoaneurysms, infections and steal syndrome) and re-intervention rates at 1 and 2 years.

3. Background

It is known that arteriovenous fistulae (AVF) confer a clear benefit for hemodialysis access in patients with end stage renal disease (ESRD). As a result, national guidelines stipulate AVF as the preferred mode of permanent hemodialysis access¹. In practice, not all patients are good candidates for AVF due to unavailable or inadequate venous conduit(s). In these patients, arteriovenous grafts (AVG) serve as reliable substitutes.

Synthetic grafts such as those made from expanded polytetrafluoroethylene (ePTFE) are the most common AVG's in current use. However, significant drawbacks of ePTFE have been reported in relation to long term patency and infection rates²⁻⁴. These inadequacies inform the need to develop and evaluate biologic conduits that achieve closer mimicry of native human vessels and as result may overcome the disadvantages associated with synthetic grafts.

Since the use of bovine carotid artery (BCA) biological grafts began in the 1970's⁵⁻⁸, significant advances have been made in conduit design and techniques for AVG placement and postoperative endovascular

management. Despite the wide spread use of ePTFE, there is lack of current evidence of a clear advantage of ePTFE over biologic conduits. Prior comparative studies were based on patient cohorts drawn from prior decades^{9,10,11}. This questions the bases for the preference of synthetic conduits in this age. In addition to this lack of current evidence, the more recent study was based on a small cohort of patients¹⁰. Consequently, these inadequately powered studies were unable to establish superiority between AVG options.

There are over 400,000 patients in the United States who are currently on hemodialysis. An estimated 110,000 new patient annually develop ESRD, requiring dialysis or kidney transplant¹². A conduit that confers better outcomes based on objective evidence will significantly impact the economy and patients' quality of life. In order to address the aforementioned knowledge gaps, we propose a prospective randomized study comparing the functional long-term outcomes between biologic and synthetic AVG conduits in a large cohort of patients. The results of this study will generate evidence needed to inform choice of AVG for permanent hemodialysis access.

4. Study Procedures

a. Study design.

Prospective Randomized Clinical Trial.

Screening

Candidates will be screened for eligibility for the study when evaluated for graft placement as per standard of care. The screening will take place in inpatient or outpatient clinic at either Johns Hopkins Bayview Medical Center or Johns Hopkins Hospital. Physical exam and preoperative vein mapping, if necessary, will be obtained to ensure the unavailability of an autogenous alternative. These surgeries will be elective in nature. Women of child bearing age will be given a urine pregnancy test preoperatively as per standard of care. Those who are pregnant or plan on becoming pregnant for the duration of the study are excluded. Candidates who meet the general inclusion / exclusion criteria will be approached for consent. All HIPAA patient privacy regulations will be observed during discussions with patients.

Consent

Patients will be recruited by the surgery services at Bayview Medical Center or Johns Hopkins Hospital. Patient history and routine preoperative tests will be used to identify comorbidities (such as diabetes, immunosuppression and smoking). Hopkins IRB approved consent designee for this study will meet with the patients prior to the operation to discuss the purpose of the trial and the subject's role, should they choose to participate. The patient will be informed in detail about the study and all their questions will be answered before signing the consent form. The patient will be given ample time to consider the study and

Will also be given a chance to review the informed consent form (ICF). They will have the option of taking the ICF home or having it mailed or emailed to them before making any decisions. No study related procedures would be performed before written informed consent process. All HIPAA privacy regulation applies here and patient rights as well as responsibilities are incorporated in the informed consent process. Consenting patients will be enrolled into the study and prospectively randomized to receive either BCA or standard ePTFE by an independent study coordinator.

Enrollment

Once enrolled, patients will be randomized to one of two groups: one group will receive the BCA graft (experimental) while the other group will receive any standard ePTFE graft (control). Randomization will be done via a computer-generated list of numbers in a 1:1 ratio using the online tool Research Randomizer.

AVG Placement

Patients will undergo surgery as per standard of care and receive the randomized graft in compliance to National Kidney Foundation Kidney Disease Outcomes Quality Initiative (KDOQI) guidelines for AVG creation¹. The grafts will be placed either in the arm (brachial artery-axillary vein) or forearm (brachial artery to cephalic or suitably sized vein) based on anatomic suitability.

Post-Operative Assessment

The patients and their grafts in both treatment arms will be monitored postoperatively per standard stipulated by KDOQI. In the immediate post-operative period, particular attention will be paid to the presence of thrills or bruits within the graft by the examiner(s) as well as neurologic and circulatory function of the ipsilateral hand. At hemodialysis the grafts will be accessed with 15 or 17 gauge needles inserted at any angle between 25-30 degrees (the same method used for a native arterio-venous fistula).

- b. Study duration and number of study visits required of research participants.

Follow-up

- 1) POD# 10-20: Physical examination by the surgeon or PA as per standard of care. Any thrills or bruits as well as any neurological or circulatory abnormalities in function of the ipsilateral hand will be noted by the examiner.

2) POD# 25-45: Physical examination by the surgeon or PA as per standard of care. Any thrills or bruits as well as any neurological or circulatory abnormalities in function of the ipsilateral hand will be noted by the examiner.

3) Thereafter; dialysis center 3 times weekly: The graft will be monitored for its functionality during dialysis sessions three times weekly by the nephrologists or trained dialysis nurses. Difficulty during dialysis (disruptions in flow pattern or increased bleeding) or the absence of a thrill or bruit will warrant surgical evaluation. If by physical examination the graft is thrombosed, then the patient will immediately be referred for endovascular thrombectomy and revision. If the graft is patent, but problematic, the patient will be referred for an urgent fistulogram and endovascular intervention.

Patients, dialysis and dialysis access centers will be contacted by the fellow or study coordinator **every three months up to two years** to ascertain function of the graft and monitor outcomes of interest.

Note: This time frame for follow up was chosen because:

- a) It will minimize data lost to follow up.
- b) It will maximize the opportunity for detection of infection, malformations or stenoses since most graft abnormalities are apparent by 30 days postoperatively.
- c) The standard of care at the Johns Hopkins surgical department includes a post-op check and visit 5 to 14 days following surgery.
- d) The follow up continues up to 2 years to report the final outcomes at end of the study.

Outcomes

Outcomes will be assessed and documented per standards for reports dealing with arteriovenous hemodialysis access¹³ and defined as follows. Primary patency: Interval from graft placement to any intervention for stenosis with or without complete occlusion (thrombosis). Assisted primary patency: interval from graft placement to the first episode of complete occlusion. Secondary patency: interval from graft placement to graft failure. Functional patency: interval from first time graft is used for hemodialysis to qualifying event as above. Infection will be defined as the presence of erythema or purulent drainage at

the surgical incision and need for intravenous antibiotics or surgical intervention. Steal syndrome will be staged per standard as follows: Stage I: pale/blue and/or cold hand without pain; Stage II: Pain during exercise and/or hemodialysis; Stage III: Rest pain; Stage IV: Ulcers/necrosis/gangrene. Accordingly, surgical intervention will be carried out for patients with stage III or IV steal.

Innovation

This study addresses the need for an objective comparison of contemporary AVG options available to patients and their surgeons. The key innovative aspects of this study are:

1. Randomization of patients to minimize the effects of measured and unmeasured confounders.
2. Study of a present-day cohort of patients so as to derive evidence applicable to contemporary practice.
3. Study of a sample of patients large enough to achieve statistical and clinically significant results.

In this study we will conduct a randomized comparison of bovine carotid artery biological grafts (Artegraft®; Artegraft, Inc., North Brunswick, NJ) to standard polytetrafluoroethylene grafts. Our goal is to establish differences in patency (functional, primary, primary assisted and secondary), complication and intervention rates.

Problems and solutions

Despite our conservative estimate, we are prepared for the possibility of inadequate enrollment in this study. In the event that we are unable to achieve a sample of patients required for well-powered analyses, we will extend patient recruitment to other hospitals on the Johns Hopkins Medical Institution network. This large back up pool of patients is reassuring.

- c. Blinding, including justification for blinding or not blinding the trial, if applicable.

This study will not be blinded because patient side blinding is expected to have minimal to no effect, while physician side blinding is impractical and difficult to achieve due to the primary surgeon being the one usually who follows up on any future interventions or treatments.

- d. Justification of why participants will not receive routine care or will have current therapy stopped.

All participants will receive routine care and will not have current therapy stopped.

- e. Justification for inclusion of a placebo or non-treatment group. **Not applicable**

- f. Definition of treatment failure or participant removal criteria.

In case of intolerance or development of an allergic reaction (such as severe incision site skin irritation or discomfort) the PI or co-PI will decide whether to remove the graft or replace it and the patient's hypersensitive reaction will be treated according to best medical practice.

5. Inclusion/Exclusion Criteria

Inclusion criteria

1. Patient must be at least 18 years of age.
2. Patient has been informed of the nature of the study, and has provided written informed consent, approved by the appropriate Institutional Review Board (IRB) / Medical Ethics Committee (MEC) of the respective clinical site.
3. Patient meets the criteria for and is undergoing Arterio-Venous-Graft surgery at Johns Hopkins Medical Institutes.
4. Patient agrees to return for all required clinical follow up for the study.

Exclusion criteria

1. Known allergic reaction or history of intolerance to any ePTFE or BCA components.
2. Local infection at AVG placement site at the time of surgery.
3. Bleeding disorder or refuses blood transfusion.
4. Presence of active malignancy and/or life expectancy is less than 1 year.
5. Patient is pregnant or plans to get pregnant for the duration of the study.
6. Any patient who is eligible to receive an Arterio-Venous-Fistula.

6. Drugs/ Substances/ Devices

- a. The rationale for choosing the drug and dose or for choosing the device to be used. Eligible vascular patient candidates who will receive the BCA graft will have improved primary, primary assisted and secondary patency as well as lower complication and re-intervention rates compared to the standard ePTFE graft.

- b. Justification and safety information if FDA approved drugs will be administered for non-FDA approved indications or if doses or routes of administration or participant populations are changed. **Not applicable**
- c. Justification and safety information if non-FDA approved drugs without an IND will be administered. **Not applicable**

7. Study Statistics

- a. Primary outcome variable.

b. Secondary outcome variables.

Complications and re-intervention rates at 1 and 2 years.

c. Statistical plan including sample size justification and interim data analysis.

All data will be stored in a secure database housed by the Vascular and Endovascular Clinical Research Center at Johns Hopkins Bayview Medical Center. Data cleaning and resolution of queries will be carried out continuously through the study period. Univariate methods (Chi Square, ANOVA, t-test) will be employed to compare patients' characteristics. Kaplan Meier and Multivariate Cox proportional regression analyses will be employed to evaluate and compare outcomes between BCA and ePTFE over time. Interim statistically analysis every 6 months between the cohorts will be performed to ensure unbiased distribution of possible confounders. If a bias is found (uneven comorbid conditions distribution), an effort will be made to correct it. All analyses will be performed using Stata version 12.1 (Statacorp, College Station, Texas). P-values less than 0.05 will be accepted as significant.

Sample Size

Specific Aims 1-3

Based on data from a prior study¹⁰ primary assisted patency of BCA was 60.5% and 40.5% at 1 and 2 years respectively. Primary assisted patency of ePTFE was 20.8 and 13.8% at 1 and 2 years, respectively. Based on an 80% power and an alpha of 0.05, the minimum sample size required to detect a 30% difference in assisted patency in a two-tailed comparison of BCA vs. ePTFE is 49 patients per group (for a total of 98 patients).

Specific Aim 4

Based on data from a prior study¹⁰, complication rates were 0.77 in ePTFE and 0.34 in BCA. Based on an 80% power and an alpha of 0.05, the minimum sample size required to detect a 30% difference in complications in a two-tailed comparison of BCA vs. ePTFE is 47 patients per group (for a total of 94 patients).

Specific Aim 5

Based on data from a prior study¹⁰, the total number of intervention for BCA was 1.45 ± 0.19 and 1.99 ± 0.25 for ePTFE⁶. Based on an 80% power and an alpha of 0.05, the minimum sample size required to detect a 20% difference in intervention rates in a two-tailed comparison of BCA vs. ePTFE is 47 patients per

Based on these estimates, this study will be conducted on a minimum sample of 100 patients with 50 patients in each treatment arm.

- d. Early stopping rules.
 - 1. Inability to tolerate BCA graft
 - 2. Allergic reaction to the BCA graft
 - 3. Statistical evidence that the BCA has better outcomes versus the standard ePTFE*

*we will carry out a review of the outcomes every 6 months in this study

8. Risks

- a. Medical risks, listing all procedures, their major and minor risks and expected frequency.

Generally speaking there is minimal risk in participating in this study. If the patient is randomized to the standard ePTFE, they will receive our hospital's standard of care for ePTFE AVG. If the patient is randomized to the BCA graft they may experience the following:

- 1. Discomfort and inability to tolerate the BCA graft: In this situation the graft will be inspected by the Principle Investigator, co-PI or wound nursing team. In the event that the patient is still unable to tolerate the graft, it will be removed or replaced and the patient will be excluded from the study.
- 2. Skin abrasion or irritation: If on inspection the skin edges at the incision site appear to be red or irritated the PI, co-PI or wound nursing team will inspect the site of operation and determine whether the graft needs revision or removal.
- 3. Allergic reaction to the device: Since BCA is an acellular collagen matrix, it is tested as non-antigenic and packaged sterile in its container. However, any foreign material may cause a reaction. If at any time during the study the patient appears to have an allergic

reaction to the BCA. The Principle Investigator or co-PI will determine if the graft needs to be removed and the patient will be removed from the study.

4. Redness or erythema, fever, signs of infection: Should there be any concern for infection of the graft, the surgery site will be assessed by the Principle Investigator, co-PI, Nurse Practitioner or Physician Assistant. Appropriate standard of care will be initiated should the wound indeed be infected. This may include opening and draining the incision, wet to dry dressing changes and antibiotics treatment.

b. Steps taken to minimize the risks.

Follow standard surgical procedures and placement of AVG.

c. Plan for reporting unanticipated problems or study deviations.

All events will be reported to the JHM IRB as required by the JHM IRB reporting guidelines posted on the JHM IRB website.

d. Legal risks such as the risks that would be associated with breach of confidentiality.

There should be no legal risks by participating in this study. None beyond those associated with routine care.

e. Financial risks to the participants.

None beyond those associated with routine care.

9. Benefits

a. Description of the probable benefits for the participant and for society.

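### Three patency measures at 1 and 2 years are all primary with no multiplicity rule, so the 5% level is not held: about 9–14% (three tests) or 15–23% (six tests) for any false difference

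*Combined protocol and SAP*

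**What the plan says.** Section 2 (Objectives) gives primary, primary assisted and secondary patency a superiority hypothesis each, every one referring to both 1 and 2 years. It then gathers them in one line: "Primary outcomes: Primary, primary assisted and secondary patency rates at 1 and 2 years". No measure or time point leads.

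Section 7c plans Kaplan-Meier and Cox analyses over time and adds "P-values less than 0.05 will be accepted as significant". It names no test for the fixed time points. It sets no testing order or adjustment for multiple comparisons, and does not say whether one, some or all of the measures must be significant.

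The sample-size paragraph labelled Specific Aims 1–3 uses a single measure: "Based on an 80% power and an alpha of 0.05, the minimum sample size required to detect a 30% difference in assisted patency". The prior-study figures are that "primary assisted patency of BCA was 60.5% and 40.5% at 1 and 2 years respectively" and "Primary assisted patency of ePTFE was 20.8 and 13.8% at 1 and 2 years, respectively". No planning figures appear for primary or secondary patency.

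The Outcomes part of section 4b starts each patency interval at graft placement, for example "Primary patency: Interval from graft placement to any intervention for stenosis with or without complete occlusion (thrombosis". It starts functional patency at first use for dialysis. The aims in section 2 speak of functional patency; the sizing paragraph does not.

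Heading 7a, for the primary outcome variable, has no text in this copy. That may be a loss in reproduction and is not counted against the plan.

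**The concern.** With several co-equal primary comparisons each judged at 0.05, a reader cannot tell in advance which result decides the trial. If any one of them is enough, the trial has several chances to produce a significant finding when the grafts do not differ, and the 5% level no longer describes the main claim. This happens even with a single final analysis. The six-monthly outcome reviews in section 7d are a separate matter and are not part of the figures below.

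The sizing shows the same gap. It covers one measure tested at the full 0.05, yet it is offered as the justification for three aims.

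**Working it through.** **1. Reproduce the plan's own figure.** The stated result is that the number needed for a 30% "difference in assisted patency in a two-tailed comparison of BCA vs. ePTFE is 49 patients per group". Take p1 = 0.605 (the 1-year BCA rate) and p2 = 0.605 − 0.30 = 0.305, with two-sided alpha 0.05 and 80% power. The mean proportion is 0.455.

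- n = [1.960·√(2·0.455·0.545) + 0.842·√(0.605·0.395 + 0.305·0.695)]² / 0.30² = 42.05, so 43 per group.
- With continuity correction: (42.05/4)·[1 + √(1 + 4/(42.05·0.30))]² = 48.5, so 49 per group.

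The stated 49 reproduces. A 30-point difference anchored on the other quoted rates gives different continuity-corrected sizes: 46 (50.8% vs 20.8%), 39 (40.5% vs 10.5%) and 41 (43.8% vs 13.8%). The sizing therefore fits one comparison based on the 1-year BCA rate, tested at the full 0.05. The plan does not state the formula or the time point; both are inferred from the match.

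**2. Count the tests.** Three measures with one test over time each make three tests. Three measures at two time points make six. The plan supports either count.

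**3. Bounds.** A two-sided test at 0.05 carries 0.025 in each direction.

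| | Three tests | Six tests |
|---|---|---|
| Any false difference, independent tests | 1 − 0.95³ = 14.3% | 1 − 0.95⁶ = 26.5% |
| False BCA benefit, independent tests | 1 − 0.975³ = 7.3% | 1 − 0.975⁶ = 14.1% |
| False BCA benefit, ceiling under any correlation | 3 × 2.5% = 7.5% | 6 × 2.5% = 15% |

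**4. Allow for overlap.** The measures are nested events in the same graft, so they are positively correlated. The documents give no correlations, so they were simulated with no true difference and 50 per arm. Event rates, correlations and loss to follow-up are assumptions.

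| Simulation | Three log-rank tests | Six tests at 1 and 2 years |
|---|---|---|
| No loss, six event-rate scenarios, 6,000 trials each: either direction | 10.9–13.6% | 19.5–23.1% |
| Same runs: false BCA benefit | 5.5–6.8% | 9.4–11.6% |
| 15% loss per year, latent correlation 0–0.9, 4,000 trials per scenario: either direction | 9.2–13.3% | 15.3–20.7% |

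Together these give about 9–14% and 15–23% in either direction. The false-BCA rate was counted directly in the first set: about 5–7% and 9–12%. By symmetry it is about half the two-sided rate, so halving the lowest values of the second set would give 9.2/2 = 4.6% and 15.3/2 = 7.7%, slightly below those ranges.

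**5. Price of adjusting instead of choosing.** Bonferroni over six tests (alpha 0.05/6 = 0.0083), at 60.5% vs 30.5% and 50 per arm:

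- With continuity correction, power falls from 81% to 57%, and 72 per arm would be needed.
- Without it, power falls from 86.5% to 65%, and 66 per arm would be needed.
- At the full prior-study 1-year difference (60.5% vs 20.8%), power would still be about 91–94%.

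**The case against.** A reader might infer that the chance of falsely declaring BCA better is 15–21% instead of 5%. The documents do not support that. The sizing describes two-tailed comparisons, so each test carries 2.5% in the BCA direction and six tests cannot exceed 15% in total, whatever their correlation. Figures of 15–21% describe a false difference in either direction. For a false BCA benefit the right comparator is 2.5%.

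Six tests are not established either. Section 7c plans comparisons over time and names no fixed-time test, so three is a fair reading. The hypotheses refer to both years, which keeps six possible.

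Nor does the plan say that any one success is enough. If all measures had to be significant there would be no inflation, although power would then need justifying for every measure.

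The missing text under 7a might have ranked the outcomes. That cannot be excluded, but the list in section 2 stands and ranks nothing.

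On the remedy, assisted patency is not free of unblinded decisions. Section 4b refers patent but problematic grafts for intervention, which can affect later occlusion. Adjustment would also be affordable if the prior-study difference held. Choosing a single outcome is therefore partly a preference, and the case for it rests mainly on the sizing.

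These points limit the size and certainty of the problem. They do not supply the missing rule.

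**Conclusion.** The concern holds in this form: section 2 sets several co-equal primary patency comparisons, section 7c gives a 0.05 threshold and no rule for combining them, and the sizing covers one measure only. If any one significant result counts as success, the chance of at least one false difference is two to nearly three times the nominal 5% with three tests (9–14%), or three to nearly five times with six (15–23%). For a false BCA benefit the corresponding figures are about 5–7% and 9–12%, against 2.5%.

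That inflation exists is firm, given the any-one-counts assumption. Its exact size is not, because it depends on the number of tests and on event rates, correlations and losses that the documents do not give.

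**What to change.** In section 2, and in 7a to match, name one primary outcome and one time point, tested at two-sided 0.05. Primary assisted patency at 12 months is the natural choice: the sizing uses that measure, and the stated 49 per group reproduces from its 1-year BCA rate.

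State whether its clock starts at graft placement or at first dialysis use, because Aim 2 says functional and the sizing does not.

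Make primary patency, secondary patency and all 24-month comparisons secondary. Either test them in a fixed order after the primary outcome or report them with confidence intervals only.

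The cost is wording in sections 2 and 7, settled before outcomes are compared between arms. No extra patients or procedures are needed. The downside is that the measures made secondary can no longer carry the headline claim alone.

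### After day 45, milder steal and pseudoaneurysm have no structured ascertainment that is independent of referral, so detection could differ by arm and favour Hypothesis 4A by an unknown amount

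*Combined protocol and SAP*

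**What the plan says.** The secondary hypothesis in section 2 is "Patients receiving BCA grafts will have lower complication rates at 1 and 2 years follow up than those who receive ePTFE grafts". The complications named are pseudoaneurysm, infection and steal.

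Section 4b schedules two clinic examinations, both of which cover the hand on the graft side. The later one is "2) POD# 25-45: Physical examination by the surgeon or PA as per standard of care". No examination is scheduled after it. Item 3 then hands routine checking to dialysis staff: "The graft will be monitored for its functionality during dialysis sessions three times weekly by the nephrologists or trained dialysis nurses". The triggers for referral to a surgeon are: "Difficulty during dialysis (disruptions in flow pattern or increased bleeding) or the absence of a thrill or bruit will warrant surgical evaluation".

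A second route follows in the same section: "Patients, dialysis and dialysis access centers will be contacted by the fellow or study coordinator", at three-month intervals for two years, to check graft function and follow the study's outcomes. The protocol gives no questions, form or checklist for these contacts.

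The Outcomes part of section 4 stages steal on hand signs and symptoms, for example "Stage II: Pain during exercise and/or hemodialysis", and defines infection partly by the treatment it needs. It does not define pseudoaneurysm. Section 4c states that the trial is unblinded.

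**The concern.** The item 3 triggers concern how the graft runs at dialysis. A cold or pale hand, hand pain, or a bulge over the graft is not on the list, although these are the findings by which steal is staged and a pseudoaneurysm would be noticed. After day 45, close examination by a surgeon therefore follows largely from graft malfunction, and the plan expects malfunction to be more common with ePTFE. If examination raises the chance that a mild complication is recorded, more would be recorded in the ePTFE arm even when the true rates are equal. That error runs in the direction of Hypothesis 4A. It cannot be repaired at analysis, because a sign that nobody looked for leaves no record.

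**Working it through.** **Plan's own figure.** Section 7c gives 47 per group for Aim 4. Two proportions of 0.77 and 0.47 (0.77 less 30 points), two-sided alpha 0.05 and power 80% give:

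- Uncorrected: n = [1.96 × √(2 × 0.62 × 0.38) + 0.842 × √(0.77 × 0.23 + 0.47 × 0.53)]² / 0.30² = 39.9, so 40.
- With continuity correction: 47, which matches.

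Aim 4 is thus sized for a 30-point difference, the yardstick for the gaps below.

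**Which arm is expected to be referred more?** Section 7c gives primary assisted patency for BCA of 60.5% and 40.5% at 1 and 2 years. For ePTFE, "Primary assisted patency of ePTFE was 20.8 and 13.8% at 1 and 2 years, respectively". Interventions are 1.45 (BCA) and 1.99 (ePTFE). At 1:1 allocation, the ePTFE share is:

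- 1-year loss of assisted patency: 79.2 / (79.2 + 39.5) = 66.7%
- 2-year loss: 86.2 / (86.2 + 59.5) = 59.2%
- Interventions: 1.99 / (1.99 + 1.45) = 57.8%

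These are stand-ins, as the documents give no referral rates.

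**Illustrative spurious gap.** Assume the same true risk p in both arms, 95% detection in referred patients and detection d in the others. With q the share referred:

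observed rate = p × [0.95q + d(1 − q)]

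gap = p × (q for ePTFE − q for BCA) × (0.95 − d)

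Worked case, p = 0.5, d = 0.6, 1-year figures:

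- ePTFE: 0.5 × (0.792 × 0.95 + 0.208 × 0.6) = 43.9%
- BCA: 0.5 × (0.395 × 0.95 + 0.605 × 0.6) = 36.9%
- Gap: 0.5 × 0.397 × 0.35 = 6.9 points

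Gap in percentage points at p = 0.5:

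| Proxy for referral | q ePTFE | q BCA | d = 0.8 | d = 0.6 | d = 0.4 |
|---|---|---|---|---|---|
| Assisted patency lost by 1 year | 79.2% | 39.5% | 3.0 | 6.9 | 10.9 |
| Assisted patency lost by 2 years | 86.2% | 59.5% | 2.0 | 4.7 | 7.3 |
| At least one intervention (Poisson) | 86.3% | 76.5% | 0.7 | 1.7 | 2.7 |

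The last row assumes Poisson counts, so q = 1 − exp(−mean). The plan gives no time period for those counts. At p = 0.3 every gap is 0.6 times as large, so the 1-year row becomes 1.8 to 6.6 points. The values of p and d and the 95% are assumptions; none is in the documents.

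**Chance of a false finding for BCA.** Let s be detection in non-referred relative to referred patients, so that observed rate = p × [q + (1 − q)s]. Take p = 34% in both arms (the plan's BCA complication rate), 50 per arm, and the patency proxies. Against a nominal 2.5%:

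| s | 1 year | 2 years |
|---|---|---|
| 0.5 | 11.4% | 7.2% |
| 0.75 | 5.5% | 4.3% |
| 1 | 2.5% | 2.5% |

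The bias disappears when detection does not depend on referral.

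**The case against.** The strongest reply is that item 3 is not the only route. Patients and centres in both arms are contacted every three months whatever the state of the graft, and the study's outcomes are part of that contact. Stages II and III steal are defined by pain, which a patient can report. Stages III and IV lead to surgery. Infection as defined needs intravenous antibiotics or surgery, which leaves a record. Increased bleeding is a listed trigger and is not purely a flow sign. Both arms are also followed to an external guideline standard, and outcomes to an external reporting standard; neither's content can be seen here. All of this stands, and it confines the weakness chiefly to stage I steal and small pseudoaneurysms. It does not remove it, because a contact without set questions recovers only what someone happened to notice and volunteer.

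The sizes are also open to challenge. The model applies the detection loss to all complications, including infection, where it is least likely. Loss of assisted patency understates referral in both arms, because patent but problematic grafts are evaluated too. The intervention-based proxy cuts the worked case from 6.9 to 1.7 points.

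Two stronger readings are tempting. A reader might infer that pseudoaneurysm and steal will be found mainly in referred patients. The documents give no detection rate outside referral. Nor would such a pattern show bias by itself: on the 1-year proxy, (79.2 + 39.5) / 2 = 59% of patients count as referred, so 59% of events would fall among them even with equal detection. A reader might also hold that the fall in patency from year 1 to year 2 refutes note b of section 4b, "since most graft abnormalities are apparent by 30 days postoperatively". It does not. Those figures concern occlusion, not steal or pseudoaneurysm, and say nothing about the first 30 days. Note d separately justifies following patients to two years.

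**Conclusion.** The concern holds as a risk of unequal detection, not as a demonstrated bias. It rests on four features of the text: no examination scheduled after day 25-45, referral triggers that name no hand or graft-wall sign, a quarterly contact without content, and an unblinded trial with no pseudoaneurysm definition in the protocol. The likely direction, towards Hypothesis 4A, follows from the plan's own expectation of more failures and interventions with ePTFE, and it holds only if referral raises detection. That excess is a modest majority (58-67%).

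The documents do not fix the size. At 50% true risk the illustrations run from 0.7 to 10.9 points, the largest being about a third of the 30-point difference for which Aim 4 is sized. Aim 4 is a secondary aim. The case for acting is that the remedy is cheap and must be in place before data are collected.

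**What to change.** Before enrolment, attach one fixed question set to the existing three-monthly contacts, identical in both arms and answered from that week's dialysis session. It should cover:

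- hand colour and temperature, pain at exercise, dialysis or rest, and ulceration, giving steal stage I-IV with onset date;
- any swelling over the graft, judged against a written pseudoaneurysm definition;
- any intravenous antibiotics, admission or surgery for the access.

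Record how each complication was first found: scheduled contact, referral or other. Keep all events in the main Aim 4 analysis. Add a sensitivity analysis restricted either to events whose capture depends least on referral (infection as defined; steal or pseudoaneurysm leading to intervention) or to status at each scheduled contact regardless of how the event was first found. Do not report a rate that counts only events first found at a scheduled contact. That would drop events first found at referral, expected to be more numerous with ePTFE, and would bias Aim 4 the other way.

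The cost is a short form, a few minutes of dialysis staff time per quarter, and more mild events recorded in both arms. It adds no visit and changes no treatment or referral rule.
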